#### C.2.c. Procedures

- **C.2.c.1. Ensuring a Robust and Unbiased Approach: Rigor and Transparency.** The proposed study will achieve robust and unbiased results via several design features including: explicit inclusion/exclusion criteria; randomization of treatment condition; placebo control; blinding; use of validated laboratory and interview/self-report measures and methods; explicit hypotheses and planned statistical analyses; power estimates; management of retention/attrition and missing data; and careful consideration of potential confounds. All experimental details are reported in a detailed and fully transparent manner to support replication.
- **C.2.c.2.** Screening and Eligibility Assessment. Individuals interested in participating will be screened by an MUSC research study intake coordinator on site at the Charleston Center, MUSC/community treatment program, Shoreline Behavioral Health or over the phone A quick screen, focused on inclusion/exclusion diagnoses, medical status, medication regimen, and ability/willingness to complete assessments and study procedures, will be used to initially determine study eligibility. Potential participants will be given a full description of study procedures and asked to read and sign an IRB-approved Informed Consent Form if they choose to participate. Inclusion/exclusion criteria are detailed below.

**Inclusion Criteria:** 1.) Able to provide informed consent and function at an intellectual level sufficient to allow accurate completion of assessment instruments. 2.) Meet DSM-5 criteria for OUD (within the past three months); while individuals may also meet criteria for another substance use disorder, they must not meet criteria for moderate or severe use of any other substance (except tobacco or marijuana) within the last 60 days. 3.) On a V20 7.25.23

stable dose of buprenorphine or methadone for 4 weeks. 4.) Age 18-60. 5.) Women of childbearing potential must agree to utilize an effective means of birth control. 6.) Must consent to random assignment.

**Exclusion Criteria:** 1.) Women who are pregnant, nursing or of childbearing potential and not practicing an effective means of birth control. 2.) Evidence or history of major medical illnesses, including liver or renal diseases, abnormal vaginal bleeding, suspected or known malignancy, thrombophlebitis, deep vein thrombosis, pulmonary embolus, clotting or bleeding disorders, heart disease, insulin-dependent diabetes, history of stroke or other medical conditions that the investigator deems as contraindicated for the individual to be in the study. 3.) History of or current psychotic disorder or bipolar I affective disorder. 4.) Current suicidal or homicidal risk. 5.) Taking any medications known to act on the adrenergic system (B-blockers, alpha agonists or antagonsits). 6.) Hypotensive individuals with a sitting blood pressure of < 90/50 mmHg 7). QTc interval of > 440 in males and > 460 in females as the combination of lofexidine and methadone may increase QTc interval. For males with a QTc of greater than >440, but less than 470 AND absence of any history of CV disease AND absence of family history of CV death, they are eligible for enrollment. For females with a QTc of greater than >460, but less than 490 AND absence of any history of CV disease AND absence of family history of CV death, they are eligible for enrollment. 8.) Known allergy to lofexidine.

C.2.c3. Screening and Diagnostic Instruments. Quick Screen: The instrument is designed to assess for substance dependence and obvious psychiatric, medical, and logistic exclusions. Mini-International Neuropsychiatric Interview (M.I.N.I) is a brief structured interview designed to assess DSM-5 diagnoses using a series of questions in dichotomous format (yes/no). The M.I.N.I. is similar in sensitivity, specificity, and interrater reliability to other lengthier diagnostic interviews, such as the SCID-I/P (Sheehan & Lecrubier, 2003; Sheehan et al., 1998). The alcohol and drug use disorder modules will be used to thoroughly assess current and lifetime diagnostic status for abuse and dependence. It has excellent inter-rater and test-retest reliability (First et al., 2002). Menstrual History Diary will be used for female participants to estimate the timing of their cycle for the 90-days prior to study entry and track during study participation. Perceived Stress Scale (PSS) is a 10-item assessment of daily stress (Cohen et al., 1983) that has previously been used in substance use research (Fox et al., 2009; Hyman et al., 2007). Adverse Childhood Experiences (ACE) Questionnaire assesses childhood maltreatment and exposure to household dysfunction. It has been utilized to examine the relationship between adverse childhood experiences and health risk behavior in adulthood (Felitti et al., 1998). The Life Stressor Checklist-Revised (LSC-R; Wolfe & Kimerling, 1997) will be used to assess for the number of exposures to various potentially traumatic life events including accidents, interpersonal violence, and death of a relative. Participants will answer yes or no for 30 potential life events. In addition to providing data to assess the impact of daily stress and early childhood trauma on opioid use, utilization of the PSS and ACE will likely allow for potential cross-SCORE collaborations as these scales have been previously recommended as components of the core assessment battery utilized across centers. Coronavirus Impact Scale: 12 item guestionnaire assesses life changes that have occurred as a result of the coronavirus (Stoddard & Kaufman, 2020). We will also ask how substance use has been impacted.

Substance-Related Instruments. Time Line Follow-back (TLFB; Sobell & Sobell, 1992) is a calendar-based instrument designed to assess daily substance consumption. Opioid use will be recorded in times used per day as well as quantity, type of opioid and route of administration. Urine Drug Screening: Urine samples will be collected and analyzed for prescribed and illicit drugs at baseline and at each study visit. All urine specimens will be analyzed using drug test cups with temperature-controlled monitoring. Drug test cups with immunoassay drug screen cards will be used to identify the following substances: oxycodone, buprenorphine, methadone, tramadol, benzodiazepines, Opiate 300 group analytes (morphine, heroin, and codeine), THC, cocaine, amphetamine, methamphetamine, ethyl glucuronide, fentanyl, K2, and MDMA. Other drugs may be detected by these analytes at high concentrations. For example, hydrocodone may be detected under the oxycodone test at high concentration levels. The cups also include adulterant testing for creatinine, nitrite, pH, bleach and specific gravity. Saliva drug screening: Saliva drug screens will be obtained from Forensic Fluids and will test for THC, cocaine, opiates, benzodiazepines, methadone, oxycodone, buprenorphine, and fentanyl. Patients will collect and store samples which will be returned to the clinic and sent to Forensic Fluids in batches. Samples will be de-identified. Inventory of Drug-Taking Situations (IDTS) (Annis et al., 1997) measures typical drug using situations based on Marlatt and Gordon's (1985) eight category taxonomy. This instrument will be used at baseline and contains eight subscales mapping frequency of use in distinct types of situations including use during negative situations (unpleasant emotions) and positive situations (social situations). Although initially developed for alcohol use, it has been modified for other SUDs and has demonstrated sensitivity to gender

differences (Ross et al., 1994). **Brief Pain Inventory (BPI)** (Cleeland & Ryan, 1994). Assesses severity of pain and impact on functioning. This measure will be completed at screening and at the end of treatment.

An EKG and physical exam including orthostatic hypotension testing will be conducted by a licensed medical provider. Serum will be collected for baseline labs and a UDS will be collected. If the participant is female, a pregnancy test will be done prior the urine drug screen. Females who are pregnant will not be allowed to participate. Participants at Shoreline will have labs drawn by Mako Medical Lab at the Shoreline site.

**C2.c4..** Remote screening visit:. Patients may also complete the initial visit remotely if warranted. In this case, subjects will be electronically consented using Doxy.me or RedCap or a combination. The informed consent will be emailed to the participant prior to the video call. The patient will have the opportunity to ask questions on the call and will electronically sign the document. A signed copy will be emailed to the participant. The M.I.N.I interview and medical history then be conducted, also via Doxy.me Patients will be advised to find a private location during these procedures to protect privacy and confidentiality. Patients will be sent survey links to complete self-report questionnaires. The blood draw, EKG and orthostatic BP will be done at Baseline. A physical exam may be done if it is warranted based on medical history. Urine drug screening and pregnancy testing will not be done until baseline for participants who screen remotely.

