1 hour follow-up period (Figure 3) suggesting greater noradrenergic stimulation in women. This finding is similar to the gender-specific pattern of response seen in cocaine-dependent individuals in an earlier SCOR study ([name] et al., 2009). Women in this study reported significantly more daily hassles and used opioids on a higher percentage of days in the one-month follow-up period as compared to men (Table 1). In addition, lower distress tolerance, measured at baseline, was significantly associated with a higher percentage of opioid use days for women (b=17.01, p=.013), but not for men. In summary, these data suggest that OUD women demonstrate greater subjective and noradrenergic stress response than OUD men. The pattern of low cortisol and high subjective response to stress exhibited by women in

this study has been associated with higher relapse in studies in cocaine dependence (Back et al., 2010). Furthermore, women reported lower distress tolerance, higher experience of daily hassles and a robust relationship between low distress tolerance and drug use. Taken

together, these preliminary findings suggest that an intervention targeting stress vulnerability, particularly through blockade of noradrenergic activation, may be particularly effective in relapse

prevention for opioid-dependent women.

[figure not shown]
C.1.d. Experience with Ambulatory Assessments. During the last funding period, the MUSC SCOR research group developed ambulatory assessment tools to assess stress

| TABLE 1: MONTH AFTER TESTING         |            |              |           |  |  |
|--------------------------------------|------------|--------------|-----------|--|--|
|                                      | Men (n=21) | Women (n=18) | Stats     |  |  |
| % days using                         | 30.4       | 55.3         | p = 0.107 |  |  |
| Daily Hassles Score                  |            |              |           |  |  |
| One Week 46.3 105.4 p = 0.018 |            |              |           |  |  |
| One Month                            | 41.6       | 87.5         | p = 0.058 |  |  |

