## C.2.c.5. Phase 1: Baseline and Medication Trial

- **a. Initial Study Visit.** Participants will be trained to use CREMA and the one-week naturalistic baseline data collection period will begin following screening procedures. If it is determined that patient is ineligible based on labwork, they will be excluded and baseline procedures will end.
- **b.** Baseline Assessment (Study days 1-7). Throughout this study period, participants will come to the clinic for UDS collection. To facilitate opioid abstinence during the baseline period, we will use a standard contingency-management procedure. Participants will earn payments of \$10 for the first negative UDS and \$20 for the second. Two consecutive UDSs during the baseline week must be negative for illicit opioids in order for the subject to enter the medication treatment part of the trial. During the baseline assessment period, participants will be asked to use CREMA (described below). Subjects may have up to 10 days to provide the negative UDSs.

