Aim 2: To evaluate the impact of lofexidine on opioid craving and subjective experience of daily stressors in men and women with OUDs: The primary measures of interest for Aim 2 are craving and stress ratings in response to stress-related cues using *Cue Reactivity Ecological Momentary Assessment* (CREMA) as well as subjective experiences of daily life stressors Hypothesis 1: Lofexidine will decrease craving and decrease the subjective experience of daily stressors in opioid-dependent men and women. Exploratory Hypothesis 2: Lofexidine will be more efficacious in decreasing stress-related craving in opioid-dependent women as compared to men. To assess this hypothesis a multilevel generalized linear mixed effects models with repeated measures (GLMMs) will be developed using CREMA session response data from the 5-week period during study medication administration. Pre-cue stress and craving rating will be centered and used as a time varying covariate in all analysis. Additionally, CREMA cue response data during the 7 day baseline assessment period will be used as a time naïve covariate in all analyses. Least squares means and associated standard errors will be used for post-hoc comparisons of craving and stress response between women and men over time. Models developed to address hypothesis 2 will be utilized to examine the impact of gender on opioid use and stress-related craving during study treatment. All other relevant interactions will be assessed in all models.

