Exploratory Aim 3: To evaluate the impact of lofexidine on illicit drug use in men and women with OUDs: Daily use data will be collected through morning reports via EMA and verified by urine drug screens (3 times weekly). Hypothesis 1: Lofexidine will increase the number of consecutive days abstinent as compared to placebo. Hypothesis 2: Lofexidine will be more efficacious in increasing consecutive days abstinent in women as compared to men. Time to relapse will be calculated as the days between the start of study medication (following titration; day 14) and the first day of lapse to opioid use or the laboratory stress induction day (day 40). Additionally, daily use data will be examined to determine the maximum number of consecutive days abstinent during follow up. Kaplan-Meier estimates and log-rank tests will be used to assess initial relationships between study treatment assignment and relapse while Cox proportional hazards models will be developed to assess the differential time to return to use across gender (using and appropriate interaction term). A significant interaction indicates that treatment may impact return to use time differently in women and men. Proportionality of hazards will be assessed using log-log plots and log-time interactions.

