## Power and Sample Size (complete sample size justification available in Biostatistics Resource Core):

The current study is powered on the primary Aims 1 and 2. In the proposed study, response to a laboratory stressor, CREMA cue response and daily use data will be tested using GLMMs (assuming a Gaussian distribution) and the study will be powered to sufficiently address the least of the study treatment effect sizes determined to be clinically meaningful for the study hypothesis. Aim 1: Sinha and colleagues (Sinha, et al 2007), in a small pilot sample, demonstrated that lofexiding in combination with naltrexone attenuated craving and anger in response to laboratory drug and stress cues as compared to naltrexone alone. Results indicate a larger change in opioid craving scores in response to drug-related and stress cues occurs in placebo participants than lofexidine treated participants [Drug related cue response  $\Delta$ =2.2; SDP=2.6; between group Cohen's d=0.85, p<0.05 and stress cues response  $\Delta$ =2.1; SDP=2.4; between group Cohen's d=0.88, p<0.05]. Moreover, Fox and colleagues (2014) conducted a trial of quanfacine in cocaine-dependent individuals and noted stress and craving response to stress and drug-related imagery. They noted significant gender differences across treatment assignment for craving and stress response to drug-related imagery [Craving  $\Delta$ =3.0; SDP=3.8; Treatment x Sex Intx Cohen's d=0.79, p<0.05; Negative Emotion  $\Delta=3.0$ ; SDP=2.9; Treatment x Sex Intx Cohen's d=1.0, p<0.05]. Sample sizes in both the Sinha and Fox studies were somewhat small. Smaller but still clinically relevant effect sizes in an adequately powered study are anticipated. Therefore, a 20% reduction in craving and stress response from the previous studies is anticipated in the current design (Cohen's d=0.64 for the sex x treatment interaction on craving response). Aim 2: Kowalczyk and colleagues (2015), showed that daily life craving reports as measured by EMA were significantly reduced in opioid using participants randomized to clonidine as compared to placebo [6.3% (95% CI=5.6-7.1) vs. 11.8% (10.9-13.0); between group Cohen's *d*=1.6]. To assess the least of the differences anticipated in project 2, a sample size of 39 participants randomized to each female and males across active lofexidine and placebo groups would provide 80% power with a type 1 error rate of 5% to detect the treatment x sex interaction in craving and stress response to laboratory drug based cues (total n=156; 78 per group). We anticipate 25% attrition between randomization and the end of the 5-week active treatment period. Thus, inflating the necessary sample size to 68 participants randomized per treatment group with a total of n=136 randomized participants will provide adequate power.

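### Exploratory Aim 3 names no baseline covariate for time to relapse although opioid use is recorded before randomisation; if prior use predicts relapse, a pre-specified adjusted Cox model would recover some power

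*Combined protocol and SAP*

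**What the plan says.** The analysis is in C.2.d under "Exploratory Aim 3: To evaluate the impact of lofexidine on illicit drug use in men and women with OUDs". For treatment, "Kaplan-Meier estimates and log-rank tests will be used to assess initial relationships between study treatment assignment and relapse". For gender, "Cox proportional hazards models will be developed to assess the differential time to return to use across gender (using and appropriate interaction term"). No baseline covariate and no stratification factor is named for either.

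The other aims do adjust. Aim 1 controls for task-level baseline craving and stress and foresees further covariate-adjusted models. For Aim 2, "CREMA cue response data during the 7 day baseline assessment period will be used as a time"-naïve covariate throughout.

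Opioid use before randomisation is available from three sources:
- **Time Line Follow-back**, in C.2.c3 among the screening instruments: "Opioid use will be recorded in times used per day as well as quantity, type of opioid and route of administration". Its look-back window and assessment day are not stated.
- **Urine screens** in the baseline period (C.2.c.5, item b). Two consecutive negatives are needed to enter the medication phase, and "Subjects may have up to 10 days to provide the negative UDSs".
- **A daily CREMA survey** of substance use (C.2.c.5, item c), used from the baseline week on.

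Randomisation is stratified on other substance use and on childhood trauma (ACE>4), as stated in C.2.c.5, item d. On power, the plan says "The current study is powered on the primary Aims 1 and 2". It gives no hazard ratio, relapse rate or event count for Aim 3.

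**The concern.** Prior opioid use is a natural candidate predictor of relapse. When a prognostic covariate is left out of a survival analysis, two things follow even if the arms are balanced. The test of treatment loses power, and the estimated hazard ratio lies nearer 1 than the hazard ratio conditional on the covariate. Any chance imbalance in prior use between arms also stays in the estimate. In a trial of 136 with about 26 days of follow-up, events will be few and avoidable loss of information is worth preventing. If the covariate is not fixed in advance, it may instead be chosen after the data are seen.

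**Working it through.** **Plan's own figure.** There is none for Aim 3, so nothing can be reproduced. I take from the documents 136 randomised at 68 per arm, a 5% type 1 error (read as two-sided), and follow-up from day 14 to day 40, so 40 − 14 = 26 days. (Table 2 has titration running to study day 17. That is a separate inconsistency with the day-14 start, and the calculation uses the Aim 3 text.) Treatment effect, relapse rate and covariate strength are assumptions.

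**Step 1: information available.** Events needed for HR 0.60 at 80% power (Schoenfeld): 4 × (1.960 + 0.842)² / (ln 0.60)² = 4 × 7.85 / 0.261, which rounds up to 121. If 25% to 60% of 136 relapse, there are 34 to 82 events. Power is Φ(½√d × 0.511 − 1.960):
- 34 events: Φ(2.915 × 0.511 − 1.960) = Φ(−0.47), about 32%
- 82 events: Φ(4.528 × 0.511 − 1.960) = Φ(0.35), about 64%

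**Step 2: effect of leaving out a predictor.** Trials were simulated with hazard proportional to exp(ln 0.60 × treatment + g × x), where x is standard normal and g = 0.3, 0.5 or 0.8 (HR 1.35, 1.65 or 2.23 per SD). Censoring was at 26 days with no drop-out, with 2,000 trials per setting. A treatment-only Cox test stands in for the log-rank test. The Monte Carlo standard error of each power is at most √(0.5 × 0.5 / 2000) = 1.1 points.

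| Control relapse | Covariate HR per SD | Power without | Power with | Gain (points) | Limiting unadjusted HR |
|---|---|---|---|---|---|
| 30% | 1.35 | 27.5% | 28.6% | 1.1 | 0.60 |
| 30% | 1.65 | 29.8% | 32.0% | 2.2 | 0.60 |
| 30% | 2.23 | 24.3% | 30.0% | 5.7 | 0.63 |
| 50% | 1.35 | 48.2% | 49.7% | 1.5 | 0.61 |
| 50% | 1.65 | 43.2% | 48.6% | 5.4 | 0.62 |
| 50% | 2.23 | 35.9% | 47.0% | 11.1 | 0.64 |
| 70% | 1.35 | 59.5% | 62.8% | 3.3 | 0.61 |
| 70% | 1.65 | 55.1% | 62.9% | 7.8 | 0.63 |
| 70% | 2.23 | 46.1% | 63.0% | 16.9 | 0.66 |

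With g = 0 the gain is nil (at 50% relapse, 47.7% without and 47.5% with).

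**Step 3: no treatment effect.** The unadjusted HR stays at 1.00, and both analyses reject in about 4% to 6% of trials.

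**Step 4: treatment-by-gender interaction.** With HR 0.9 in men and 0.5 in women, 50% relapse and 1,500 trials per setting, power moves from 20.1% to 20.8%, from 17.4% to 19.7% and from 16.5% to 19.8% for the three covariate strengths.

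**Step 5: sensitivity to drop-out and effect size.** With 25% drop-out, 55% control relapse, conditional HR 0.50 and 2,500 trials per setting, power goes from 68% to 70%, 66% to 70%, 60% to 71% and 53% to 72% for log-HRs of 0.3, 0.5, 0.7 and 1.0 per SD. With HR 0.60 the gains are 2, 5, 9 and 15 points. The direction and order of size agree with Step 2.

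**The case against.** Several objections have force.

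- **The gain is conditional.** A reader might infer that power is certainly lost. The documents do not show this: they report no association between prior use and relapse. All participants are on stable maintenance and must pass two negative screens under contingency management, so use in the baseline week varies little. Only a longer Time Line Follow-back window could carry much information, and the simulated covariate is normal and measured without error, which a self-reported day count is not. This objection stands, and the size must be given as a range that starts near zero.
- **The hazard ratio is not biased.** A reader might take a value nearer 1 as bias. It is non-collapsibility: the unadjusted HR is a valid marginal estimate, and the log-rank test keeps its size (Step 3).
- **The pilot does not show heavier prior use in women.** It says women "used opioids on a higher percentage of days in the one-month follow-up period as compared to men" (55.3% against 30.4%, p = 0.107). That is use after testing, so it cannot serve as evidence of a baseline difference. Treatment is also randomised, so a main effect for prior use is not needed to remove confounding within each gender.
- **Aim 3 is exploratory, and the fuller plan was not supplied.** C.2.d refers to a complete plan in the Biostatistics Resource Core, and Cox models that are still to be developed do not exclude covariates. The absence of adjustment is therefore read from silence. That limits the weight of the point. It does not remove it, because the Aim 3 text names a specific unadjusted test while the neighbouring aims state their baseline adjustment.

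**Conclusion.** The point holds as an inexpensive improvement to an exploratory analysis. Aim 3 is the only aim whose text names no baseline adjustment, although a baseline measure of the same behaviour is collected. If prior use is prognostic after the entry gate, adjustment recovers about 1 to 3 points of power for a weak predictor (HR 1.35 per SD), 2 to 8 for a moderate one (1.65) and 6 to 17 for a strong one (2.23). This assumes a conditional HR of 0.60 and 30% to 70% control relapse. For the gender interaction the gain is about 1 to 3 points on a base of 17% to 20%, so the number of events is the larger limit there. The unadjusted HR would tend to 0.60 to 0.66 where the conditional HR is 0.60. No stated power is invalidated, and type 1 error is not in question.

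**What to change.** In the Aim 3 text of C.2.d:

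1. Make the main treatment analysis a Cox model with treatment, gender, one pre-specified baseline opioid-use measure, and the two stratification factors (other substance use, ACE>4).
2. Define the measure as Time Line Follow-back opioid-use days over a stated look-back window that ends before the baseline week. State the window and assessment day in C.2.c3 as well.
3. Keep the same covariates in the treatment-by-gender model.
4. Keep the Kaplan-Meier curves and the log-rank test, stratified if feasible, as supportive.
5. Do not use any positive urine screen before randomisation as a covariate unless it is defined on a fixed set of screens common to all participants. Remote screeners have no urine test until baseline (C2.c4), and those who use the full 10 days may give more samples, so the variable would partly measure screening route and sample count.
6. If the Biostatistics Resource Core plan already adjusts Aim 3, say so in C.2.d.

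The interaction model then has six terms: treatment, gender, their interaction, prior use and two factors. At about 58 events that is 58 / 6 = 9.7 events per term, and at 34 events it is 5.7, which argues against adding more.

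The cost is a few sentences, including a decision on the look-back window. No new visits, participants or data are needed.
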